If appropriate describe secondary or post hoc analyses of primary outcome(s) or other exploratory analysis and if necessary, provide a breakdown of the methods used per outcome or endpoint:

Statistical Method to Inform Randomization Bias: Intent to treat bias. To establish equivalence of randomly assigned groups pre-intervention, t-tests will be performed on outcome measures comparing the groups. Means and standard deviations will be obtained and effect sizes calculated. Demographic profiles will be obtained and bivariate significant tests performed to assess the balance expected with randomization. Cohort effects on outcome as well as participation rates will be evaluated to assess any bias related to location, calendar time, or other session characteristics. Participation rates across the intervention will be tracked and compared between the randomized groups. In the spirit of the intent to treat principle (White, Carpenter, and Horton 2012) every effort will be made to conduct follow-up assessments on all randomized participants. Withdrawals will be documented with reason provided. In addition, multi-level modeling allows all cases to remain in a repeated measures model and will be done as a sensitivity analyses to primary analyses done on individuals with at least one follow-up point.

Sample Size Determination: Explain how the overall target sample size was determined (e.g., power analysis; precision estimation), providing justification of the effect size for the primary outcome based on preliminary data, current knowledge/literature and/or cost consideration; if appropriate, provide sample size justification for secondary outcomes. Power analysis should (at least) match the primary outcome/endpoint:

Sample Size. This exploratory study will employ a parallel-group randomized clinical trial design in which 48 participants will be randomly allocated to one of two (2) treatment/intervention groups (AAI and Control) delivered across four (4) cohorts in two (2) waves over the span of two (2) years ($n = 12$ per parallel ten-week cohort) in efforts to inform the specific aims of the study.

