Power & Expected Effect Size. Sample size analysis was conducted for randomized controlled design, using SAS PROC power. For the primary analysis of the main outcome domain (Aim 1: ADHD Behavior) with type I error rate of .05 was implemented for a repeated measures analysis evaluating group main effect, treatment main effect, as well as the group*treatment interaction. Effect size estimates from the authors' previous parallel-group randomized study of HAI demonstrated large AAI vs control effect size for problem behaviors (.86) and moderate effects on inattention (.45) ([name] et al., 2018a). For Aim 1, with a projected analysis of $n=48$, this exploratory study will exceed 90% power to detect effect sizes of .19 and above. At a level of 80% power, the minimum detectable effect was determined to be .21. For Aim 2, $n = 48$ will, for each of the two primary physiological outcome domains (Aim 2: Diurnal Pattern Hypothalamic Pituitary Adrenal axis activity; HPA and Autonomic Nervous System activity; ANS), a multilevel model will be constructed to assess pre-post intervention change, post-follow up change, group differences at each assessment, and group differences in degree of change. Models will account for within-subject correlation and within-cohort correlation. Four (4) cohorts of 13 participants each will be recruited for a total enrolled target sample size of 52 families over Years 1 and 2, accounting for an anticipated attrition rate of about 8% which is based on our recently completed study of AAI with ADHD ([name], et al., 2018a) in efforts to yield a total sample of 48.

Research Procedures

Provide a detailed chronological description of the clinical or treatment plan:

See Study Design

List all procedures involving the use and/or collection of photographs, or audio/video recording:
Facial image will be in video or photo Participants' first names may be collected or recorded in either video or audio recording

Specify the total duration of a subject's participation in the study and clearly outline the duration of participation for each study visit and sub-study, as applicable:

See Study Design

List data collection tools (e.g., measures, questionnaires, observational tool) below by clicking the 'Add Line' button. Include additional rows for study instruments, as needed:

The 'Columns' button allows you to display or hide columns in the Study Instrument List.

Name of Tool:

The Child's Sleep Habits Questionnaire (Owens, Spirito, & McGuinn 2000)

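### Both arms are treated in weekly play groups, but the Aim 1 primary test and its power name no play-group or cohort term; the 5% error rate is not protected if children in the same play group change together

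*Combined protocol and SAP*

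**What the plan says.** **Delivery.** Under Study Design, eligible children attend weekly group sessions of about two hours. These play groups run with or without up to 3-4 dog/handler dyads. Under Sample Size, 48 children are randomly allocated to AAI or control, "delivered across four (4) cohorts in two (2) waves over the span of two (2) years". That section puts 12 children in each cohort and calls the ten-week cohorts parallel.

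**Aim 1.** Under Power & Expected Effect Size, the sample-size analysis for ADHD behaviour "with type I error rate of .05 was implemented for a repeated measures analysis evaluating group main effect", a treatment main effect and their interaction. With n=48, "this exploratory study will exceed 90% power to detect effect sizes of .19 and above". The prior trial is said to have "demonstrated large AAI vs control effect size for problem behaviors (.86) and moderate effects on inattention (.45").

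**Aim 2.** In the same section, for the two physiological domains "a multilevel model will be constructed to assess pre-post intervention change, post-follow up change", and group differences. The next sentence reads: "Models will account for within-subject correlation and within-cohort correlation".

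**Supporting analyses.** Under Statistical Method to Inform Randomization Bias, multilevel modelling is described as a way to keep all cases and "will be done as a sensitivity analyses to primary analyses done on individuals with at least one follow-up point". Also, "Cohort effects on outcome as well as participation rates will be evaluated to assess any bias" related to location, calendar time or other features of the sessions.

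The text available does not give the number, size or arm composition of the play groups. Figure 1 (cited under Specific Aim 1 but not shown) or the attached Protocol Narrative may.

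**The concern.** Children in one play group share sessions, peers and, in the AAI arm, dogs and handlers. The plan's second hypothesis is that the quality of in-session social interaction mediates outcome. If so, children who share sessions may tend to change together. An arm comparison that counts 48 independent children then has too small a standard error and too many error degrees of freedom.

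Aim 1 is the replication claim, and the only aim with a type I error rate and power figures. What is at stake is whether a difference produced by one or two unusually cohesive, or unusually difficult, play groups could be reported as an effect of dogs.

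**Working it through.** **1. The plan's own power figures.** The plan gives more than 90% power at .19 and a minimum detectable effect of .21 at 80% power. These run in the wrong order, since the effect detectable at 80% power cannot exceed the one detectable at 90%. The metric is not stated.
- Read as standardised mean differences with 24 children per arm, two-sided, .19 and .21 give 9.6% and 10.9% power.
- Read as Cohen's f for group-by-time (three occasions, assumed within-child correlation .5, 48 independent children), they give 81.8% and 89.1%. The minimum detectable f is .186 at 80% and .213 at 90%.

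On the second reading the figures resemble an independent-children calculation with the two power labels exchanged. That depends on the assumed correlation. The inversion is a separate defect; what matters here is that no reading found brings in a design effect.

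**2. Inputs for the size check.** From the plan: 48 children, two arms, three visits, nominal 5%. Assumed: 24 per arm, two-sided tests, equal play groups, ICC 0 to .10, and three layouts: 8 groups of 6, 4 of 12, 12 of 4. The last is included because the IRB Amendment form reports 8 children in active intervention, which is only a snapshot.

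**3. Hand check on change from baseline.** Let m be the group size, k the number of play groups and r the ICC of change. The variance of the arm contrast is multiplied by 1+(m-1)r. The pooled child-level variance, on 46 df, has expectation [(k-2)(1+(m-1)r) + (48-k)(1-r)]/46.
- 8 groups of 6, r=.05: 1+5(.05) = 1.25; pooled variance (6×1.25 + 40×.95)/46 = .989; ratio 1.264. The critical value 2.013 acts like 2.013/√1.264 = 1.79, so the true size is about 8.0%.
- 4 groups of 12, r=.05: 1+11(.05) = 1.55; pooled variance (2×1.55 + 44×.95)/46 = .976; ratio 1.588. The effective critical value is 1.60, so the true size is about 11.7%.

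**4. Three-visit group-by-time F test (2, 92 df).** The plan's group-by-treatment interaction is read as group-by-time. This is a null simulation, 20,000 datasets per cell, with a play-group effect arising after baseline, ICC on the post-baseline score and within-child correlation .5:

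| Layout | ICC 0 | .02 | .05 | .10 |
|---|---|---|---|---|
| 8 groups of 6 | 5.1% | 6.0% | 7.9% | 11.1% |
| 4 groups of 12 | 4.9% | 7.4% | 11.5% | 18.9% |
| 12 groups of 4 | 5.1% | 6.0% | 6.5% | 8.7% |

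At ICC .05, within-child correlations of .3 to .7 give 6.9-10.3%, 9.2-15.7% and 6.1-7.8% respectively.

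**5. Effect constant over all visits.** It cancels from group-by-time (4.9-5.2%). It does not cancel from the group main effect that the plan also lists: 6.8/9.3/13.3% (8 of 6), 8.8/15.0/23.5% (4 of 12) and 6.2/7.7/10.0% (12 of 4) at ICC .02/.05/.10.

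**6. Would a cohort term suffice?** If each cohort holds both arms (8 groups of 6), adding cohort as a fixed effect to the test of pre-post change moves the size from 7.8% to 8.1% at play-group ICC .05, and from 11.1% to 11.7% at .10. A cohort effect shared by both arms cancels; an arm-specific play-group effect does not. If each cohort is one single-arm play group, cohort and play group are the same level.

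**7. What holds 5%.** A t-test on play-group mean changes stayed at 4.7-5.2% in every layout. A random play-group model with variance bounded at zero gave 3.1-4.6% (8 of 6) but 3.1/4.4/6.0/7.1% (4 of 12) at ICC 0/.02/.05/.10.

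**8. Price in power, as an illustration only.** Read .86 as a standardised difference on the analysed change. The noncentrality is .86×√12 = 2.98, divided by √(1+(m-1)r).
- 48 independent children (46 df): 83%.
- 8 groups of 6 (6 df): 70% at ICC 0, 61% at .05.
- The same groups paired within four cohorts (3 df): 53% and 45%.
- 4 groups of 12 (2 df): 38% and 28%.

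From the critical t alone, intervals widen by 2.45/2.01 = 1.22 (6 df), 3.18/2.01 = 1.58 (3 df) and 4.30/2.01 = 2.14 (2 df).

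**The case against.** The best defence is that the plan already deals with clustering. The within-cohort sentence speaks of models in the plural and carries no aim label. The mediation text, whose example outcome is behavioural change, mentions multilevel models. Cohort effects and session characteristics are to be examined. With 12 children per parallel cohort and two cohorts per wave, each cohort could be one single-arm play group, which would put the within-cohort term at the right level. The trial is also called exploratory.

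Part of this stands. The team recognises clustering, and the gap may close with a short clarification. But the sentence sits directly after the Aim 2 model, the bias section gives multilevel modelling only a sensitivity role, and the mediation text describes the primary analysis as having treatment group alone. The exploratory label lowers the stakes, yet the plan still attaches a .05 error rate and power to Aim 1.

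Three stronger readings are tempting but unsupported:
- **That the Aim 1 error rate is in fact inflated.** No ICC is given, and at ICC 0 the test is correct.
- **That the within-cohort term is at the wrong level.** The layout is not in the text available, and parallel cohorts may be single-arm.
- **That the trial's real power is 70% or 38%.** Those figures rest on one reading of .86 and are not the plan's stated power.

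**Conclusion.** The point holds as a conditional one. As written, Aim 1 has no stated allowance for play-group correlation in its primary test or its power. The condition for harm is that changes of children within the same play group are positively correlated. Under the assumptions above (ICC .02 to .10, within-child correlation .5, effect arising after baseline), the nominal 5% group-by-time test runs at about 6-11%, 7-19% or 6-9% for 8 groups of 6, 4 of 12 or 12 of 4. A constant effect harms only the group main effect. Layout and ICC drive the size entirely, and both are assumed. The change should be made, with medium confidence that it matters in this trial.

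**What to change.** 1. State, or point to, the number, size and arm composition of the play groups. Say that the clustering allowance applies to Aim 1 too, at the level of the play group attended, acting on change from baseline, with small-sample df. If a random play-group model is used, check its size by simulation for the actual layout. If each cohort is one single-arm play group, extend the existing within-cohort term to Aim 1, but not as a fixed effect, because it would be aliased with arm. If cohorts hold both arms, a cohort term alone is not enough.
2. If the layout leaves only 2-3 df, present the estimate with its cluster-adjusted interval and keep the child-level test as a sensitivity analysis. A group-level significance test need not be required. Say that arm and play-group effects can then hardly be separated.
3. State that the Aim 1 power figures assume independent children. Show power with 1+(m-1)×ICC and the reduced df over ICC 0 to .10, on the change scale, for the actual group size.

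**Cost.** No new data or enrolment; play-group membership should be on record. The Progress Report says no data had been analysed at that renewal, so the rule could be set in advance; if analysis has since begun, label it as added afterwards. The price is the wider intervals and lower power shown above. With so few groups the ICC will be poorly estimated: at a true ICC of .05, the bounded model put the play-group variance at zero in 35-42% of runs.

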This project explores physiological mechanisms thought to underlie the positive effects of AAI for children with ADHD and posits that interaction with dogs during treatment improves social behavioral and physiological outcomes and that individual differences in bio-markers and interaction style mediate outcomes for this group. **Rationale & Background** Despite decades of research aimed to optimize outcomes for children with ADHD, the condition remains a significant public health problem adversely impacting individuals, families and schools. The annual cost of ADHD is estimated at \$266 billion (Doshi et al., 2012). Pharmacotherapy (e.g., methylphenidate) is the mainstay of traditional medical intervention for ADHD, but treatment failures are common (Caye, Swanson, Coghill, & Rohde, 2018; Schneider & Ennenbach, 2014; Swanson et al, 2018), and affected children often require medications during what are now recognized as critical periods of growth and development. It is not surprising that parents find alternative therapies, including Animal Assisted Intervention (AAI), to be more acceptable than medication (Rabbit, Kazdin, & Hong, 2014). Our research found AAI to be effective in reducing ADHD symptoms and improving social skills and self-perception ([name] et al., 2015; [name] et al., 2018a, [name] et al., 2018b). **Gaps in Current Knowledge** While we demonstrated the effectiveness of AAI for this group, the underlying mechanisms of these effects is unknown; a critical gap in our developing body of evidence for AAI needed to increase the acceptability and accessibility of this integrative health care strategy. The research proposed in this application will break ground in this nascent area and contribute to the rapidly developing discipline of HAI research by (1) contributing to our understanding of bio-social mechanisms which may underlie outcomes, (2) identifying individual responses thought to mediate outcomes and (3) informing the development of future large scale, multi-site trials aimed to informing best practices for delivering AAI in special pediatric populations and improving accessibility to this practice.

Provide relevant preliminary data (animal and/or human):

N/A

Describe the primary outcome variable(s), secondary outcome variables, and predictors and/or comparison groups as appropriate for the stated study objectives/specific aims:

N/A

List up to ten relevant references/articles to support the rationale for the research:

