The proposed research will run a Parallel-Group Randomized Controlled Trial, employing an exploratory parallel-group randomized controlled trial study design and utilizing a multi-method and multi-source assessment protocol. a. The study is currently planned to take place at The Children's School at [name] b. We will use a repeated-measure within-subject design, gathering measurement of main outcomes at three time points to assess the efficacy of AAI for children with ADHD who are participating in a short-term intervention with or without the assistance of therapy dogs. A linear, repeated measures design will be utilized for our primary, and exploratory main outcome. c. Over the course of about 4 months, children will participate in treatment and assessment for a total up to approximately 16-20 hours) and parents will participate in approximately 6-9 hours of assessment. d. Children and their parents will first attend a screening visit that will last 2-3 hours to determine eligibility. e. If eligible, participation will require participants to attend group sessions for integrative, non-medical treatments for ADHD, once weekly (one weekday after school to be determined as space permits for about 2 hours per session (for a total of about 16-20 hours). These play group sessions may or may not include the participation of up to 3-4 certified therapy dog/handler dyads. These group sessions will be video recorded to capture child-child, child-dog, and dog behavior. f. Participation will also require child participants to attend three (3) Saturday "Laboratory School" assessment visits, immediately prior to and after the intervention period and then five weeks later. Each of these assessments will last approximately five to six (5-6) hours (about 18 total hours over three visits) for child participants and up to 2 hours each of three visits for parents (about 6 hours total). "Laboratory School" recess sessions will be video taped to capture observed child-child interactions. g. Participants will also be requested to wear a device used to collect heart rate (FirstBeat monitor) during the assessment days (3) and intervention sessions (3) and on the night prior to participation in the three (3) Saturday "Laboratory School" assessment visits. The FirstBeat monitors which have been found to be acceptable, feasible, safe and reliable for collection in several youth samples. For heartrate collection, parents will be instructed on how to affix a

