Statistical Method per Outcome Specific Aim 1: Replicate Previous Favorable Behavioral Response to AAI Primary Main Outcome: Behavior responses. This parallel-group randomized design and will utilize a multi-method and multi-source assessment protocol. The assessment protocol will use a repeated-measure within-subject design, gathering main outcomes at three time points to assess the efficacy of AAI on outcomes for children with ADHD who are participating in a short-term intervention with or without the assistance of certified therapy dogs (see Figure 1). Our previous research indicated that after just 2 weeks of intervention, participants in the AAI condition showed significantly greater improvement in symptoms compared to control participants and that these gains were maximized by 10 weeks and then maintained at 6 weeks post intervention ([name] et al., 2018a), suggesting that 10 weeks is an ideal duration of treatment to detect significant benefits from AAI with dogs. Outcomes from AAI utilizing a manualized treatment with therapy dogs (AAI) will be compared to standard of care evidence-based psychosocial treatment at usual (control). Specific Aim 2: Determine Physiological Response over time to AAI for children with ADHD. Exploratory Main Outcome: Diurnal HPA and ANS responses. To determine if children with ADHD present with measurable changes in physiological responses to a short-term AAI (10 weeks) on measures of HPA and ANS we will gather candidate salivary analytes (salivary cortisol, uric acid, and alpha-amylase; Cort, sUA, sAA, respectively) and measures of cardiac rhythm, (heart rate variability; HRV) prior to and post intervention for children participating in both treatment conditions before, immediately after, and upon treatment follow up. Specifically, for each domain we will ascertain changes in diurnal patterns of candidate physiological measures utilizing a linear, repeated measures design gathered across three (3) points in time; establishing individual baseline patterns, end of treatment patterns, and then patterns at 6 weeks post-treatment. Specific Aim 3; Explore Individual Differences as potential mediators of response to AAI in children with ADHD. Secondary Outcome Exploratory Mediator Analysis; In the proposed study, we will explore how children's individual (a) acute physiological responses during intervention sessions and their individual (b) social interaction quality during intervention sessions may play a role in each of the Main Outcomes. Specifically, we will a) ascertain acute HPA activity (as measured by Cort, and sUA) and acute ANS activity (as measured by HRV and sAA) during intervention sessions across

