
both treatment conditions and we will b) ascertain the quality of in-session social relationships (child-child) across both treatment conditions as well as the quality of in-session child animal interaction (child-dog) during the AAI sessions (observed child/child & child/dog interaction) at three (3) time points across the 10-week study intervention period (weeks 1, 5, & 10). The acute response and interaction quality measures from each of the three sessions will then be correlated with the degree of change in the primary main outcomes. (e.g., pre-post change in ADHD symptoms, social skills, regulation) and the exploratory main outcomes (e.g., pre-post change in diurnal HPA activity and ANS activity) to examine the potential mediation of individual differences on response to AAI with therapy dogs for children with ADHD. Here we provide an example of one mediation analysis for treatment group (AAI vs Control) as the primary predictor, salivary cortisol response slope at session 5 the potential mediator, and behavioral change (pre-post change) the outcome: First, cortisol response slope² means will be compared between the groups (the mediator must be related to the predictor). If significant, then the relationship between cortisol response slope², and behavioral change will be evaluated for a significant correlation/slope (the mediator must be related to the outcome). Finally a model will be run with both treatment group and cortisol response slope² predicting behavioral change. If the relationship between treatment group and behavioral change is reduced compared to the primary analysis (i.e., with treatment group alone), saliva cortisol response² is interpreted as providing a mediated effect. To obtain estimates of the size and significance of the indirect effects, bootstrapping procedures as described by Shrout and Bolger (2002) will be implemented. Due to the fact that bootstrapping procedures are still limited in the case of multilevel models, an approximation of the Sobel test will also be performed, along with Monte Carlo estimation of confidence intervals but because this aim is exploratory and this is not a fully powered study, results presented will include descriptive and confidence intervals.

Describe the statistical method(s) that will be used to analyze the primary outcome(s) or endpoints:

see previous section

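### Aim 1 does not say which effect is the efficacy test, and the unadjusted change contrast it points to is usually less precise than a baseline-adjusted one

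*Combined protocol and SAP*

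**What the plan says.** All references are to the combined protocol and SAP.

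- **Power & Expected Effect Size.** Aim 1 is sized for a "repeated measures analysis evaluating group main effect, treatment main effect, as well as the group*treatment interaction". None of the three effects is singled out. The section claims more than 90% power for effects of .19 and above with 48 children, and a minimum detectable effect of .21 at 80% power. It gives neither the effect-size metric nor a correlation between visits.
- **Specific Aim 1 (statistical methods).** The design is described as "gathering main outcomes at three time points to assess the efficacy of AAI on outcomes for children with ADHD". The result to be replicated is that "participants in the AAI condition showed significantly greater improvement in symptoms compared to control participants".
- **Specific Aim 3.** The primary main outcomes are exemplified as "pre-post change in ADHD symptoms, social skills, regulation". The worked mediation example takes pre-post behavioural change as the outcome and refers back to a primary analysis whose only predictor is treatment group.
- **Study Design.** The three assessment visits fall "immediately prior to and after the intervention period and then five weeks later", so a baseline value is already collected. Aim 2 instead places the last visit at six weeks: "end of treatment patterns, and then patterns at 6 weeks post-treatment".
- **Fields that could have settled the matter.** "Describe the primary outcome variable(s), secondary outcome variables, and predictors and/or comparison groups as appropriate for the stated study objectives/specific aims" is answered N/A. The endpoint-definition field refers the reader to the text above it. "Describe the statistical method(s) that will be used to analyze the primary outcome(s) or endpoints" refers back to the preceding section.
- **Randomization-bias paragraph.** Baseline outcome values are compared between arms by t-test. No Aim 1 text uses them as a covariate or in a common-baseline model.

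**The concern.** The three listed effects answer different questions. The group main effect averages over all visits, including the one before treatment, so it dilutes any treatment effect. The second effect, labelled treatment, presumably means time, and by itself does not compare the arms. The interaction, presumably group-by-time, captures differential change, which is what the Aim 1 and Aim 3 wording suggests.

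Two things are at stake. With the test unnamed, power depends heavily on which effect is eventually reported, and the choice could be made after the results are seen. And in a trial of 48 children, an unadjusted change contrast usually gives up precision that the baseline measurement could supply at no cost.

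**Working it through.** **The plan's own figures.** As printed, the smaller effect (.19) has more power (over 90%) than the larger (.21, at 80%), which no single fixed test can give. Read as standardised mean differences with 24 per arm, .19 and .21 give about 10% and 11% power. Read as Cohen's f for a group-by-time interaction over three visits, with an assumed correlation of .5 (noncentrality f²·48·3/(1−r), 2 and 92 df), they give 82% and 89%. The two labels may have been exchanged, but without a stated metric and correlation the figures cannot be reproduced.

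**Inputs.** From the documents: 48 analysed, alpha .05, three visits, and a prior effect of .45 for inattention. Assumed, because the documents do not give them: 24 per arm, two-sided test, equal variances across visits, compound symmetry, no clustering, .45 in single-visit outcome SDs, and baseline-to-outcome correlation r = .3, .5, .7 or .8.

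**Formulas.** The SE of the arm contrast is √(V·2/24), where V is in units of the outcome variance:

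- Change to post-treatment: V = 2(1−r), 46 df.
- Baseline-adjusted post-treatment: V = (1−r²)(1+1/44), 45 df. The last factor allows for estimating the slope.
- All-visit group main effect: the variance of a three-visit mean is (1+2r)/3, and a sustained effect d becomes 2d/3. On the scale of d this gives V = (9/4)(1+2r)/3.

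Example at r = .5. Change: SE = √(1.00·2/24) = .289, noncentrality .45/.289 = 1.56, power 33%. Adjusted: V = .75·45/44 = .767, SE = .253, noncentrality 1.78, power 41%.

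| | r=.3 | r=.5 | r=.7 | r=.8 |
|---|---|---|---|---|
| V, change | 1.40 | 1.00 | .60 | .40 |
| V, adjusted | .931 | .767 | .522 | .368 |
| Variance ratio, adjusted/change | .66 | .77 | .87 | .92 |
| Power, change | 25% | 33% | 50% | 68% |
| Power, adjusted | 35% | 41% | 56% | 71% |
| 80% detectable d, change | .98 | .83 | .64 | .52 |
| 80% detectable d, adjusted | .80 | .72 | .60 | .50 |
| Power, all-visit main effect | 29% | 24% | 21% | 19% |

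A simulation of 20,000 trials per correlation gave adjusted power of 34.9/42.0/55.9/70.9%. A change analysis would need about 48/ratio = 72/63/55/52 children to match 48 with adjustment.

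**Mean of the two later visits, effect sustained.** Power is 32/42/62/80% for change and 52/57/71/84% adjusted. With adjustment, this mean beats post-treatment alone only if the follow-up effect is at least 57/63/68/70% of the post effect.

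**How far the gain depends on the assumptions.**

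- *Treatment-group clustering.* Treatment is delivered in group sessions, in four cohorts of 12. Assume eight groups of six and an added group variance of .05 of the outcome variance (illustrative). This adds 2·.05/4 = .025 to the variance of the contrast, or .30 to V, whichever analysis is used. Keeping 46 and 45 df, power becomes 22/27/36/45% for change and 28/31/39/46% adjusted: gains of about 6/5/3/2 points.
- *Unequal SDs.* With post SD k times baseline SD, the ratio is k²(1−r²)/(k²+1−2rk), times 45/44. For k = 1.25 it is .80/.91/1.00/1.02. For k = .8 it is .51/.58/.64/.65.
- *Effect metric.* If .45 is in change-SD units, change power is 33% at every r, and the gain runs from about 13 points at r = .3 to about 2 at r = .8.

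**The case against.** The strongest reply is that the plan is not silent. The Aim 3 example treats pre-post change as the outcome and treatment group as the sole predictor of the primary analysis, which points to one arm contrast. That stands in part: the specification is loose rather than absent. But the cue sits in an example for a different aim and does not match the list of three effects in the power section. The separate Protocol Narrative and the measures attachment are not part of this document, so the gap is claimed for this document only.

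It can also be said that change versus baseline adjustment is purely a choice of efficiency, and that the benefit rests on a correlation, an SD ratio and an effect metric that the documents do not give. That stands, and it is why the gain is stated as conditional.

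A reader might infer three stronger things, none of which is supported:

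- That the planned analysis is biased. Under randomisation the change contrast is unbiased.
- That adjustment is always more precise. At r = .7 or .8 with a post SD 1.25 times baseline there is no gain, and slightly less precision at .8.
- That adjustment would rescue the stated power. If .21 is in SD units, 80% power needs a correlation of about .97 under either analysis.

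**Conclusion.** The point holds in conditional form. Aim 1 lists three effects, names none as the efficacy test, and has no baseline adjustment in this document. Under the stated assumptions and d = .45, adjusting the post-treatment contrast raises power by about 10/8/6/3-4 points at r = .3/.5/.7/.8. The gain is useful at low to moderate correlations, small at high ones, and further reduced by clustering within treatment groups.

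Naming the contrast matters at least as much. At r = .5, with a sustained effect, the analyses considered here run from 24% power (all-visit main effect) to 57% (adjusted mean of both later visits) on the same children. The all-visit main effect is a poor efficacy test at every correlation examined. This is a recommended improvement to a valid design, not an error that invalidates it.

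**What to change.** In Power & Expected Effect Size, and by cross-reference in the Aim 1 methods:

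1. Make the efficacy test one AAI-versus-control contrast on one named measure at one named time point. Post-treatment fits the pre-post emphasis of Aim 3; the sponsor may instead name the mean of both later visits if the effect is expected to be largely sustained.
2. Estimate it from a repeated measures model adjusted for the baseline value (as a covariate, or through a common-baseline model), with visit, arm-by-visit and cohort terms, and allow for clustering by treatment group within cohort.
3. State that the all-visit group main effect is not the efficacy test, and correct the group-by-treatment label to group-by-time.
4. Replace the .19 and .21 statements with power for that contrast, giving the effect-size metric and a range of assumed correlations.
5. Reconcile the follow-up timing (five weeks in Study Design, six in Aim 2) before any later visit enters the contrast.

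A minor wording point: baseline t-tests at 24 per arm cannot establish equivalence, since any observed difference up to t(.975, 46)·√(2/24) = .58 SD is non-significant. The means, SDs and effect sizes already planned are enough as description.

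No visits, children or data are added, and the Progress Report states that nothing has been analysed. The real cost is that the restated power for d = .45 may be well below the 90% now claimed.
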